Study Protocol and Statistical Analysis Plan (SAP)

Official Title: Smartphone-based Mindfulness Training for Health Following Early Life Adversity

(Brief Title: Remote Mindfulness Training Following Early Life Adversity)

ClinicalTrials.gov ID (NCT number): NCT05516108

Protocol Date: 08/18/2022

Study Purpose

Early life adversity (ELA) confers potential lifelong health complications, and interventions are needed to mitigate risk. Mindfulness-based interventions (MBIs) have shown promise for improving mental health outcomes among adults exposed to childhood trauma, but whether MBIs can offset physical health risk is unknown. This two-arm, parallel-group, randomized trial aims to investigate the feasibility and acceptability of remote mindfulness and coping interventions among emerging adults who recall a history of childhood trauma with the goal to inform an efficacy trial examining stress-related health outcomes.

Overview

Adults with a history of ELA will be recruited (n=80). Participants will one week of baseline ambulatory stress ratings (5x daily), continuous mobile sensor data (e.g., heart rate, activity, and location from wearable devices and smartphones), and blood samples to assess inflammatory biomarkers (e.g., IL-6, CRP, TNF-a, IL-8, IL-10). Participants will then be randomly assigned to a 14-lesson smartphone-based (a) mindfulness intervention or (b) structurally matched active control intervention that trains common coping skills, both boosted with practice prompts randomly delivered throughout the day to permit retrospective evaluation of JIT prompts. Ambulatory and sensor data will again be collected during the intervention and for one week at post-intervention and one-month follow-up, and inflammatory biomarkers will be assessed at post-intervention and follow-up. Participants will be surveyed about the acceptability of mobile data collection and intervention delivery.

Study Objectives

This trial aims to evaluate the feasibility, acceptability, and preliminary effects of smartphone-based mindfulness and control interventions among emerging and young adults with a history of ELA. Two primary hypotheses will be tested:

- The interventions and assessments will meet feasibility and acceptability benchmarks in this sample, including recruitment targets, safe implementation, and intervention/assessment adherence and fatigue.

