- Mindfulness training is expected to reduce daily life stress, normalize stress biology, and reduce markers of inflammation from pre-intervention to post-intervention and one-month follow-up.

Exploratory aims involve (1) developing machine learning models to estimate daily life stress from passive sensor data and (2) using these models to inform future JIT intervention.

Methods

Participants:

80 participants will be recruited. English-speaking adults (ages 18-29 years) who report moderate-to-severe physical, emotional, or sexual abuse in childhood (based on Childhood

[figure not shown]
Trauma Questionnaire thresholds) and own data-enabled Android or iOS smartphones will be recruited in Pittsburgh. Those with severe mental health diagnoses (e.g., psychosis) will be excluded for safety. The sample is expected to be 65% white, 30% black, 5% other race; 5% Hispanic; and 50% female.

Recruitment:

Participants will be recruited for a study testing smartphone stress reduction programs, primarily through The University of Pittsburgh Pitt+Me research registry has nearly 30,000 potential participants ages 18-29. Interested participants will be pre-screened online for preliminary eligibility, then invited for an in-person baseline eligibility screening and visit.

Procedures:

Data will be collected across an 8-week study period as follows:

Lab visits include blood draw and questionnaire assessments. Ecological Momentary Assessment (EMA) includes surveys delivered at four random times daily and end-of-day diary assessments. Mobile sensor data collection includes AWARE phone sensor and Fitbit data.

T1: Baseline. Participants will attend a study visit to confirm eligibility, provide informed consent, complete psychosocial assessments, and prepare for the at-home assessments and intervention. Dried blood spot (DBS) samples will be collected to assess inflammatory biomarkers. During a one-week ambulatory stress assessment, participants will provide four ecological momentary assessments (EMA) and one evening diary survey daily assessing stress and resilience; stress physiology (HR) and activity (e.g., steps, sleep) via wearable device; and smartphone sensor data.

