T2: Two-week intervention. Following baseline assessments, participants will be randomly assigned to the mindfulness intervention or coping control intervention condition. Participants will complete one 20-minute audio-guided lesson each day, plus receive 3 brief text-based practice prompts daily at random times. The interventions were developed by [name] and [name] and are matched on attentional demand, lesson length and structure, and voice. Interventions will be delivered via smartphone app that securely tracks participant activity, including timestamps at lesson and practice prompt start/completion and daily survey responses (stress assessments pre- and post-lesson, pre- and post-practice prompt, and each evening; practice prompt receptivity). This data will be integrated with phone sensor and wearable data to inform future JIT intervention tailoring. Staff will check in with participants on intervention days 3, 9, and 14 to provide support and monitor for adverse events.

Mindfulness intervention: Based on [name]'s Unified Mindfulness system, lessons train meditation techniques for 3 mindfulness skills: (1) concentration, a stable attention on present-moment body experiences; (2) sensory clarity, the detection and discrimination of sensory experiences; and (3) equanimity, an attitude of acceptance and receptivity toward present-moment experiences. Practice prompts build on the skills trained in each lesson, encouraging participants to practice brief moments of mindful awareness, mindfulness while doing daily tasks, or formal meditation for 5-10 minutes.

Coping control intervention: To parallel the structure of the mindfulness intervention without training present-moment attention or acceptance skills, participants are instructed to: (1) reflect and mind wander; (2) reappraise past and future events; and (3) analyze and solve personal problems. Practice prompts encourage participants to take brief mind-wandering breaks, apply reappraisal or problem-solving skills, or reflect for 5-10 minutes. This program controls for nonspecific effects (e.g., goals, daily practice, and treatment expectancies). Here, an active control program will inform the feasibility of the RCT design for future trials and will preempt differential dropout issues that are commonly seen in studies using no-treatment control groups.

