2. Self-reported diagnosis of chronic mental disorder (e.g., schizophrenia, personality disorder, or psychotic illness) major neurological disorder, or suicidal thoughts or wishes at baseline
3. Medication use that interferes with HPA-axis activity (e.g., corticosteroids) or autonomic activity (e.g., antihypertensive medication)
4. Current antibiotic, antiviral, or antimicrobial treatment
5. Shift workers
6. Pregnancy or breastfeeding
7. Excessive alcohol use
8. Frequent illicit drug use
9. Regular systematic mind-body practice (>2 times per week)

Statistical Analysis Plan (SAP)

Power:

Sample size balances rules of thumb for pilot trial sample size (which range from 25-35 participants per treatment arm estimating a small between-group effect size, with larger pilot trials more accurately estimating variance and allowing for smaller sample sizes in efficacy trials) with calculations to detect medium within-group effects of mindfulness on EMA stress ($d=.40$). Therefore, we plan to enroll 80 participants (40 per condition).

Statistical Analysis Plan:

This study will evaluate two primary aims and one exploratory aim:

Aim 1 evaluates the feasibility and acceptability of the interventions and assessments, with the prediction that interventions and assessments will meet feasibility and acceptability benchmarks in this ELA sample, and mindfulness and control groups will show equivalence on these measures.

- Planned analysis: Feasibility and acceptability will be evaluated by comparing screening and enrollment numbers, participant retention, adherence to intervention and assessment protocols, treatment expectancies, intervention fatigue, and prompt timing to proposed benchmarks for success. Specifically, minimum feasibility benchmark ranges are as follows: 10% of those screened will be eligible; 60-70% of eligible participants will enroll; <10% of participants will show increases in daily stress, a measure of safe implementation; 80-90% of enrolled participants will be retained through the intervention period and 75-85% through the follow-up assessment period; participants will complete 85-95% of the intervention lessons, 60-70% of practice prompts, 75-90% of ambulatory assessments, and provide mobile sensor data on >75% of days. ANOVAs will test for equivalence of mindfulness vs. control groups on

feasibility and acceptability outcomes.

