Aim 2 tests for mindfulness intervention changes to establish effect sizes for a future RCT, with the prediction that mindfulness training will reduce daily life stress, normalize stress biology, and reduce markers of inflammation from pre-intervention to post-intervention and one-month follow-up.

- Planned analysis: MLMs will be used to test for mindfulness intervention changes in daily life subjective stress events and perceptions, stress-related HR in daily life (HR during high stress surveys relative to average person-centered HR), and markers of inflammation from pre-intervention to post-intervention and one-month follow-up. Secondary MLM analyses will test for mindfulness intervention changes in daily life resilience (positive/negative affect; social factors) and daily life HRV. Tertiary MLM analyses will test for between-group differences (mindfulness vs. coping intervention) on all outcomes.

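### Aim 2 appears to lead with change inside the mindfulness arm and ranks the randomised mindfulness-versus-coping contrast as tertiary

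*Combined protocol and SAP*

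**What the plan says.** Study Objectives announces "Two primary hypotheses will be tested". The second reads "Mindfulness training is expected to reduce daily life stress, normalize stress biology, and reduce markers of inflammation", over time and with no comparator named.

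In the Statistical Analysis Plan, the purpose is given as "Aim 2 tests for mindfulness intervention changes to establish effect sizes for a future RCT". The planned analysis has three tiers:

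- **Lead:** "MLMs will be used to test for mindfulness intervention changes in daily life subjective stress events and perceptions", and likewise for stress-related heart rate and inflammatory markers, from baseline to post-intervention and one month.
- **Secondary:** the same kind of test for resilience outcomes and heart rate variability.
- **Tertiary:** "Tertiary MLM analyses will test for between-group differences (mindfulness vs. coping intervention) on all outcomes".

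The Power paragraph rests on pilot rules of thumb and on "calculations to detect medium within-group effects of mindfulness on EMA stress" (d = .40). That is the only numerical effect it gives.

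On the control arm, the section on the coping intervention says "This program controls for nonspecific effects (e.g., goals, daily practice, and treatment expectancies", with the parenthesis closing there, and adds "Here, an active control program will inform the feasibility of the RCT design for future trials".

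**The concern.** Change from baseline in one arm is the sum of any effect specific to mindfulness and everything else that moves over the same weeks: time, repeated stress surveys, expectancy, and the effect of doing some structured daily programme. The coping arm is there to remove those shared components, and only the between-arm contrast uses it.

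Two things are at stake. First, a significant fall in the mindfulness arm could be reported as support for the second primary hypothesis even if the coping arm fell just as far. Second, Aim 2 attaches its effect-size purpose to the changes it ranks first. If that figure is carried into planning a two-arm trial, it overstates the between-arm effect whenever coping training also helps.

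**Working it through.** **1. The text.** Taken alone, the wording of the lead models could mean a time-by-condition effect. Three features point the other way. The tertiary line covers all outcomes, so it would merely repeat the tiers above it. The power basis is expressly within-group. The second hypothesis names no comparator.

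**2. The plan's own figure.** The plan enrols 80, or 40 per condition. Alpha, sidedness, target power and pre-post correlation r are not stated, so the figure cannot be reproduced uniquely. Using a one-sample t-test on change, with noncentrality d√n and alpha 0.05:

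- d = .40 in SD-of-change units, n = 40: power 69% two-sided, 80% one-sided.
- d = .40 in raw SD units with assumed r = .6: d becomes .40/√(2 × 0.4) = .447, and 42 are needed for two-sided 80% power.

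So 40 fits a within-arm calculation under some unstated assumptions. As a between-arm effect (noncentrality d√(n/2)), d = .40 at 40 per arm has 42% power.

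**3. What the within-arm test does when mindfulness has no specific effect.** Assume both arms change equally by c, in SD-of-change units (c is my assumption). The test is two-sided at 0.05. The first two rows come from the noncentral t; the last two from simulation with 40 per arm and 40,000 trials per cell.

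| | c = 0.1 | 0.2 | 0.3 | 0.4 |
|---|---|---|---|---|
| Within-arm significant, n = 40 | 9.5% | 23.5% | 45.7% | 69.4% |
| Within-arm significant, n = 32 (80% retention benchmark) | 8.5% | 19.5% | 37.6% | 59.2% |
| Arm contrast significant | 5% | 5% | 5% | 5% |
| Within-arm significant, contrast not | 7.6% | 21.5% | 43.3% | 66.7% |

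If a shared change of 0.2 is instead in raw SD units, dividing by √(2(1 − r)) gives within-arm rates at n = 40 of 18%, 24%, 36% and 50% for r = .3, .5, .7 and .8.

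**4. What follows if the within-arm figure is used for planning.** Suppose mindfulness changes by .40. A two-arm trial sized on .40 needs 100 per arm for 80% power. If coping changes by .10, .20 or .30 (assumed), the true contrast is .40 minus that amount:

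| Coping change | True contrast | Power at 100 per arm | Per arm for 80% |
|---|---|---|---|
| .10 | .30 | 56% | 176 |
| .20 | .20 | 29% | 394 |
| .30 | .10 | 11% | 1571 |

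**5. Precision of the contrast in this trial.** The 95% half-width is t × √(2/n). At 40 per arm it is 1.991 × √(2/40) = 0.445. The post-intervention retention benchmark of 80–90% leaves 32–36 per arm (0.500–0.470). The follow-up benchmark of 75–85% leaves 30–34 (0.517–0.484). The difference detectable with 80% power at 40 per arm is about 0.63.

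All figures use one change value per person, an approximation to a mixed model fitted to repeated surveys.

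**The case against.** The strongest reply is that the within-arm reading is an inference. The SAP does not define the changes it tests or list model terms, so the lead models might include both arms. That is a fair limit on certainty about the model. It does not touch the tertiary ranking, which is explicit, and the same rewording would settle the doubt.

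Second, the contrast is planned for all outcomes, so the estimate a future trial needs will exist. This stands: the defect lies in which result leads and how it will be read.

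Third, this is a feasibility pilot with about 42% power for a between-arm d of .40, so a modest rank for that test may seem sensible. Low power is a good reason to present an interval rather than a test. It is not a reason to lead with a different quantity, and the plan itself calls Aim 2 primary.

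Fourth, the shared-change and coping-arm values are assumptions, and no text says the future trial will be sized on the within-arm effect. Also true; the tables in steps 3 and 4 are illustrations, not forecasts for this trial.

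**Conclusion.** The concern holds and should be fixed. As written, the ranking would let the second primary hypothesis be counted as supported by change that the coping arm shares, which sets aside the control the design provides. The size of the problem depends on shared change, which the documents do not give. Over assumed values of 0.1 to 0.4 SD, the chance of a significant within-arm result with no mindfulness-specific effect runs from about 10% to 69% at 40 per arm, against 5% for the randomised contrast.

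The conclusion rests on the natural, though not the only possible, reading of the lead models. It does not imply that the sample is too small for a pilot.

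**What to change.** - Fit both arms together in the planned mixed models. Make the arm-by-time contrast (T1 to T3 and T1 to T5), with its 95% CI, the primary Aim 2 estimate for the outcomes now listed first. T1 precedes randomisation, so it is a valid common baseline.
- Describe it as the effect of mindfulness relative to coping training.
- Report change within each arm side by side, as descriptive.
- State that the interval is for estimation and is not the only planning figure for the future RCT.
- For consistency, add the comparator to the second hypothesis, and say in the Power paragraph that the within-group d = .40 does not power the between-arm contrast. If the lead models were always meant to be time-by-condition, say so and give the model terms.

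The cost is SAP wording and a reordering of analyses already planned, with no new data, visits or participants. The drawback is a wide headline interval. The coping programme also trains reappraisal and problem-solving, so the contrast may be small. A small contrast should not be read as showing no benefit of mindfulness over doing nothing, a comparison this design does not make.

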Exploratory aims involve developing machine learning models to estimate daily life stress from passive sensor data and lay the groundwork for future JIT intervention. First, machine learning models developed to estimate daily life stress from passive sensor data aim to have at least 80% accuracy and 70% recall. We will use the open-source RAPIDS pipeline to extract aggregated behavioral features. We will approach stress detection as a binary classification problem where each interval prior to a random EMA is assigned a value of 0 (low stress) or 1 (high stress) based on perceived stress rating and sensor features from that interval are used to predict class membership. We will use the RAPIDS pipeline to evaluate different cross-validation approaches (e.g., leave-one-out) as well as different machine learning algorithms (e.g., random forests, extreme gradient boosting machines). Methods will be evaluated in an iterative and exploratory manner to determine which yields the best performance with regard to accuracy and interpretability. We will examine overall accuracy, precision (i.e., positive predictive value), recall (i.e., sensitivity), and area under the receiver operating characteristic curve (AUROC) in evaluating model performance. Second, MLMs will test whether mindfulness practice prompts delivered at high stress times (operationalized as being ≥ 1 SD above the person-centered stress mean) reduce state stress and end-of-day stress each day during the intervention. These exploratory analyses will inform the design and implementation of a tailored JIT intervention in a future trial.

Finally, analyses will be run separately by sex to examine potential patterns hidden in pooled analyses.

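### The stress-detection label has no stated cut-point or reference, and the 80%/70% success criterion cannot tell recognising who is stressed from recognising when

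*Combined protocol and SAP*

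**What the plan says.** All of this is in the exploratory-aims paragraph of the SAP.

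- **Purpose.** Passive sensor data are used to estimate daily stress, as preparation for later just-in-time (JIT) prompting.
- **Label.** "each interval prior to a random EMA is assigned a value of 0 (low stress) or 1 (high stress) based on perceived stress rating". No cut-point is given. The text does not say whether the cut is common to all participants or set within each person.
- **Targets.** The models "aim to have at least 80% accuracy and 70% recall".
- **Metrics.** "We will examine overall accuracy, precision (i.e., positive predictive value), recall (i.e., sensitivity), and area under the receiver operating characteristic curve". The level of computation (over all observations, or per participant) is not stated, and no baseline is named.
- **Validation.** Several cross-validation schemes will be tried, with leave-one-out as an example. The unit left out, participant or observation, is not stated.
- **Selection.** "Methods will be evaluated in an iterative and exploratory manner to determine which yields the best performance with regard to accuracy and interpretability".
- **Prompt analysis (second exploratory analysis).** High-stress times are "operationalized as being ≥ 1 SD above the person-centered stress mean".

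The prompt analysis therefore has an explicit person-relative definition of high stress, and the classifier has none.

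**The concern.** Choosing the moment for a prompt is a within-person task: on this day, is this person more stressed than usual? Overall accuracy and recall do not isolate that. If the cut is pooled, part of the variation in the label is between people, and a model can earn credit from stable sensor features (routine, sleep, phone use) that mark habitually stressed participants, without detecting anything about the moment. The listed metrics would not reveal this.

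At stake is how a reported success is read. The plan says these analyses will shape a tailored intervention in a later trial. Meeting, or nearly meeting, 80%/70% could be taken as evidence that the model can time prompts when it had not been tested for that. With two definitions of high stress, the moments the model learns to flag may also differ from those at which the prompt analysis assesses benefit.

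**Working it through.** The 80% and 70% are targets without a derivation, so there is no figure of the plan's to reproduce. The check asks how close a classifier with no information on timing can come.

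**Inputs from the documents.** 80 participants (Power); four random EMAs a day for one week at each of T1, T3 and T5 (Procedures, Measures), so 4 × 7 × 3 = 84 per person; ambulatory completion of 75–90% (Aim 1), so at least 0.75 × 84 = 63 labelled intervals per person at the lower benchmark.

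**Assumed, not in the documents.** Normal ratings; share of rating variance between persons (ICC) 0.3–0.6; prevalence of high stress 50% to 16%; SD in the prompt rule taken as the person's own.

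**Step 1: pooled cut, person mean known, nothing else.** Rating X = u + e, with Var(u) = ICC and Var(e) = 1 − ICC. The label is high when X exceeds a common cut, with prevalence p. The score flags the share q of observations with the highest person means; its correlation with X is √ICC. With TP the joint probability of flagged and high:

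- recall = TP / p
- accuracy = 1 − q − p + 2·TP

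Take the best accuracy subject to recall ≥ 70%. At a median cut this has a closed form, accuracy = recall = 0.5 + arcsin(√ICC)/π; at ICC 0.5 that is 0.5 + 0.25 = 75%. Worked case at ICC 0.6, p = 0.30: q = 0.311, recall 0.701, TP = 0.210, accuracy = 1 − 0.311 − 0.30 + 0.420 = 0.809.

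| ICC | 50% high | 30% high | 16% high | Pooled AUROC, 50% to 16% |
|---|---|---|---|---|
| 0.3 | 68.4% | 68.7% | 70.9% | 0.753–0.779 |
| 0.4 | 71.8% | 73.3% | 76.4% | 0.795–0.822 |
| 0.5 | 75.0% | 77.3% | 81.0% | 0.833–0.860 |
| 0.6 | 78.2% | 80.9% | 84.9% | 0.869–0.893 |

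Within-participant AUROC is 0.50 throughout, by construction. Both targets are met from ICC about 0.65 at 50% prevalence, 0.63 at 40% and 0.57 at 30%; at 16% they are already met at ICC 0.5.

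**Step 2: simulation check.** 80 persons × 63 ratings, median cut, leave-one-observation-out, prediction from the person's own label rate, 200 replicates. Accuracy is 67.8%, 71.1%, 74.3% and 77.6% at ICC 0.3, 0.4, 0.5 and 0.6, close to the first column.

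**Step 3: imperfect recovery of person level.** If sensors recover a fraction R² of between-person variance, replace ICC by ICC × R². With ICC 0.6 and R² 0.5 (assumed), the effective ICC is 0.30 and accuracy 68–71%. With R² 0.3 it is 0.18 and accuracy 62–64%.

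**Step 4: overlap of the two definitions.** The correlation of X with the standardised within-person deviation is √(1 − ICC). With a pooled top-16% cut, the share of moments high by the prompt rule that are also high by the model's label is 59%, 53% and 48% at ICC 0.4, 0.5 and 0.6. With a pooled median cut, only 30%, 29% and 28% of model-high moments are high by the prompt rule.

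**Step 5: person-centred label at ≥ 1 SD.** Prevalence is 1 − Φ(1) = 15.9%. A person-only rule has nothing to use: flagging 70% of moments blindly gives 0.70 × 0.159 + 0.30 × 0.841 = 36% accuracy. But always predicting *low* gives 84.1% accuracy at 0% recall, so accuracy of 80% alone proves nothing. Exactly 80%/70% would need specificity (0.80 − 0.70 × 0.1587)/0.8413 = 82%, with precision 0.111/(0.111 + 0.152) = 42%.

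**The case against.** A reader might infer that the plan uses a raw, common cut. It does not say so: a person-centred cut is also a cut based on the rating, so what is shown is an undefined label, not two contradictory definitions. A reader might likewise infer that all metrics are pooled over people. The word *overall* leans that way for accuracy, but the level is not stated.

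The figures in Step 1 are ceilings. The planned model uses sensor features from the interval, not the person's true mean. Recovering half the between-person variance at ICC 0.6 leaves accuracy about 9–12 points short of 80%. Even with perfect recovery, ICC 0.4 misses 80% at every prevalence shown. Leaving out whole participants would also stop the model learning a person's own label rate, although stable sensor features could still carry differences between people.

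It would be too strong to say the model would miss the moments the prompt analysis evaluates. Under a pooled cut the two sets overlap by roughly half. Nor does the prompt analysis use the model's output: prompts in this trial arrive at random times, so neither analysis is invalidated by the mismatch.

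These points limit the size and certainty of the problem. They do not supply a criterion that measures timing: under any of these readings, no within-person metric or baseline is named.

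**Conclusion.** The concern holds in this form: the 0/1 label lacks a cut-point and a reference, while the prompt analysis is person-centred, and the success criterion cannot distinguish between-person from within-person discrimination. The documents do not support the claim that the targets would be met without momentary information. That needs a pooled cut, an ICC of about 0.57–0.65 at prevalence of 30–50% (about 0.5 at 16%), and near-complete recovery of person level from sensors. The ICC and prevalence are not given, and the calculation assumes normal ratings. The supportable statement is that, under a pooled cut, the targets could be approached through differences between people, with at most 68–71% accuracy at ICC 0.3, rising to 78–85% at 0.6. The model's high-stress moments would then often differ from those of the prompt analysis.

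Severity is modest. The aim is exploratory, Aims 1 and 2 are unaffected, and no prompt in this trial is triggered by the model. It still merits a change, because the result is meant to inform the next design and the remedy needs no new data.

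**What to change.** 1. Define high stress for the classifier by the same person-centred rule as the prompt analysis, and say whose SD is used.
2. Make within-participant AUROC the main evidence for timing: compute it per participant, average, and give a participant-level bootstrap confidence interval. State how participants whose ratings fall in only one class are handled.
3. Report the 80%/70% figures beside two baselines: a person-average-only model and a majority-class rule. Centring alone is not enough, because always predicting *low* already gives about 84% accuracy under a ≥ 1 SD label with normal ratings.
4. State the cross-validation unit, participant or observation.

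The cost is a few sentences in the SAP and a few lines of code. The downside is that reported performance will look less favourable than under a pooled label and overall accuracy.

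### The stress classifier's validation scheme and algorithm may both be picked on performance with no nested selection or reserved participants specified, so its score against the 80%/70% targets will tend to be too high unless nesting is used

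*Combined protocol and SAP*

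**What the plan says.** The exploratory part of the Statistical Analysis Plan describes models that estimate stress from passive sensor data and gives them numerical goals: they "aim to have at least 80% accuracy and 70% recall". Each interval before a random EMA is "assigned a value of 0 (low stress) or 1 (high stress) based on perceived stress rating"; no cut-off is given, and the plan does not say whether the rating is centred on the person. The team will "evaluate different cross-validation approaches (e.g., leave-one-out) as well as different machine learning algorithms", both being open lists. The selection rule follows: "Methods will be evaluated in an iterative and exploratory manner to determine which yields the best performance with regard to accuracy and interpretability".

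The second exploratory analysis, on practice prompts, does define high stress, as at least "1 SD above the person-centered stress mean". The plan does not say whether that definition also applies to the classifier.

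On use of the results it says: "These exploratory analyses will inform the design and implementation of a tailored JIT intervention in a future trial". The closing paragraph adds that "analyses will be run separately by sex". Since the Participants section expects "5% Hispanic; and 50% female", each by-sex model would rest on about 40 people.

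Neither the protocol nor the SAP mentions nested cross-validation, a test set, participants reserved from selection or a fixed candidate list. Nor do they say whether leave-one-out removes a participant or a single record.

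**The concern.** Two things are left open to choice on performance.

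The first is the algorithm. When several candidates are scored on the same data and the best is kept, its score includes the luck that helped it win. Its performance in new people will on average be lower, whichever scheme did the scoring.

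The second is the validation scheme. A scheme is the measuring instrument, not a candidate model, and choosing it by its result favours the more flattering one. If records rather than people are split, the same person appears in training and test data. If the label also reflects who is generally more stressed, a model can score by recognising the person rather than the moment.

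At stake is whether the 80%/70% comparison can be trusted when a JIT intervention for new people is designed from it. A model slightly short of a target could appear to reach it.

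**Working it through.** The targets are goals without a derivation, so there is no figure in the plan to reproduce. The check asks how large the excess could be.

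**Inputs from the documents.** 80 participants (SAP, Power). Four random EMAs a day (Procedures) for one week at each of T1, T3 and T5: 4 × 7 × 3 = 84 intervals per person. At the lower completion benchmark of 75% (SAP, Aim 1), 84 × 0.75 = 63. About 40 people per by-sex model.

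**Assumed inputs.** The plan gives no number of candidates, label prevalence or between-person spread. Assumed: K = 2 candidates (two algorithms are named as examples) or 5-20; true accuracy 0.75; between-person SD of accuracy 0.05-0.15; correlation ρ between candidates' scores 0.5-0.8.

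**1. Selection among equally good algorithms**

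SE = √[SD²/N + p(1−p)/(N × 63)]

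- N = 80: √(0.05²/80 + 0.1875/5040) = 0.0083; with SD 0.15, 0.0178.
- N = 40: 0.0117 and 0.0252.

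Excess = E[max of K standard normals] × SE × √(1−ρ), where E[max] is 0.564, 1.163 and 1.867 for K = 2, 5 and 20.

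- Smallest, N = 80, K = 2: 0.564 × 0.0083 × √0.2 = 0.21 points.
- Largest, N = 80, K = 20: 1.867 × 0.0178 × √0.5 = 2.36 points.

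| People | K = 2 | K = 5 to 20 |
|---|---|---|
| 80 | 0.2-0.7 points | 0.4-2.4 points |
| about 40 | 0.3-1.0 points | 0.6-3.3 points |

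**2. Chance of appearing to reach 80% accuracy when the truth is 78%** (N = 80, 200,000 draws, SE recomputed at 0.78)

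- One pre-named method: 0.01-0.13.
- Best of 2: 0.01-0.21.
- Best of 5-20: 0.02-0.59.

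**3. Candidates that are not equally good.** With one at 78% and four at 76% (N = 80), the winner's excess over its own true accuracy is 0.0-1.0 points and the chance of reaching 80% is 0.01-0.15. With the four at 75%, the excess is 0.0-0.5 points.

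**4. Choice of scheme.** Simulated: 80 people × 63 intervals, random forest, 5 folds, intraclass correlation (ICC) of ratings 0.3 or 0.5, high-stress prevalence 30% or 50%.

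Uncentred label, features that identify the person but carry no momentary stress signal:

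| Share of records traceable to the right person | Record-level minus participant-level accuracy | Record-level accuracy minus majority class |
|---|---|---|
| 11-33% | −0.2 to 2.9 points | −2.1 to +0.5 |
| 54-89% | 1.1 to 10.8 points | −0.1 to +8.0 |
| 99% | 1.9 to 16.7 points | +0.9 to +14.4 |

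With a momentary signal added and the label still uncentred, the gap was 0.9-8.6 points. Both targets were falsely passed in 1 of 14 settings: accuracy/recall 81.3%/80.2% with records split, against 77.0%/76.3% with participants held out.

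With the label set at 1 SD or more above the person's own mean, the gap was 0.0-0.7 points.

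**5. Baseline.** Under that person-centred label and normal ratings, always predicting low stress is right in Φ(1) = 84.1% of intervals, with zero recall.

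**The case against.** **The plan does not exclude nesting.** Its list of cross-validation approaches is open, and a nested scheme could be among them. Interpretability is a criterion as well as accuracy. This stands: a reader might infer that the score is certain to be optimistic, and the text supports only that it will tend to be so unless nesting is used. The gap is still worth closing, because the only selection rule written down is best performance.

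**The selection figures lean on unfavourable assumptions.** The plan names two algorithms, and equally good candidates give the largest bias. This also stands. The 0.59 probability needs 20 candidates, the wider between-person spread, the lower correlation and a true accuracy only two points below target. It also counts accuracy alone, whereas the plan pairs accuracy with recall.

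**The leak is conditional.** It is tempting to read the 17-point gap as the expected error. It needs a record-level split, an uncentred label and features that almost perfectly identify people. The plan commits to none of these, and its prompt analysis uses a person-centred definition. If whole participants are left out, the leak does not arise.

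**The 84% figure does not void the targets.** An always-low rule fails the 70% recall target, and precision and AUROC are also reported. The figure supports showing a baseline and nothing more.

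**The aim is exploratory, in a pilot.** The targets are aspirations with no go/no-go decision attached, and a JIT tool might be personalised. This limits the weight of the point. It does not remove it, because the results are meant to shape a later trial.

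**Conclusion.** The point holds in a limited form. The plan lets both scheme and algorithm be chosen iteratively for accuracy and interpretability, without specifying nested selection or reserved participants. Unless nesting is used, the score set against 80%/70% will tend to be too high.

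The direction follows from the stated rule; the size rests on assumed inputs. Choosing among algorithms adds a fraction of a point with the two the plan names, and at most about 2.4 points with 80 people or 3.3 with about 40 over the range examined. It adds less when candidates differ in quality. A larger inflation requires both a record-level split and an uncentred label; otherwise that part is negligible.

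A reader might infer that the trial's main conclusions are compromised. The documents do not support that: the effect is confined to the exploratory classifier, its by-sex versions and the future JIT design. Aims 1 and 2 do not use it. This is a cheap improvement of modest weight.

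**What to change.** Before analysis, add a few sentences to the SAP that:

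- define the classifier's label, with its cut-off and whether it is person-centred;
- name one validation scheme with whole participants held out in the outer loop, and make all algorithm, feature and threshold choices in the inner loop;
- judge the 80% and 70% targets only on the outer-loop result, shown beside a majority-class baseline;
- label other schemes and algorithms as exploration, along with any personalised model in which a person's earlier days predict later ones.

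If nested selection is already intended, stating it meets most of this. The cost is the added text and more computing time. Reported performance will probably be lower. Data collection does not change.
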